3.1.1 Main Study

The study design schematic for the main study is provided in [Figure 3.1-2](#).

This is a phase 4, open-label, prospective, pragmatic clinical trial to assess the difference between all-cause hospitalizations in patients using Abilify MyCite (for Months 1-3, then prohibited for Months 4-6) versus virtual matched controls from baseline to Day 180.

Virtual matched controls ^{CCI} [REDACTED] would be receiving treatment as usual (ie, any product other than Abilify MyCite, which may be oral aripiprazole or any other product).

Eligible patients will enter a screening period of up to 13 days. For patients enrolling into the study, those not on aripiprazole at screening will use the screening period for conversion to aripiprazole from other antipsychotics according to the approved labels. At the baseline visit (which may be the same visit as the screening visit), Abilify MyCite onboarding will be provided in the office, with commercial informational materials and additional call center support; then, patients will initiate 3 months of treatment with Abilify MyCite at the baseline visit.

During the following 3 months (Months 4 through 6), use of Abilify MyCite will be prohibited (and the patient continues with oral aripiprazole or other appropriate treatment, per routine clinical care). The primary endpoint will be assessed at Day 180. The final study visit will be on Day 180 for patients not continuing in the second, optional interventional period.

After the visit at Day 180, a second, optional interventional period (up to 6 months of Abilify MyCite) may be initiated per the joint decision of the patients with their study physician; patients in this second, optional interventional period will have a visit at Day 360 (in addition to their regular visits as clinically indicated). During this second, optional interventional period, patients may start and stop Abilify MyCite as clinically indicated.

Enrolled patients will be matched to a virtual control group identified from ^{CCI} [REDACTED] in a 1:3 ratio (enrolled patients on Abilify MyCite treatment versus virtual matched controls).

^{CCI} [REDACTED]
[REDACTED] the matching will be performed after the Abilify MyCite arm has been completed.

3.1.2 Exploratory Study

The study design schematic for the parallel exploratory study is provided in [Figure 3.1-3](#). The parallel exploratory study will utilize a different set of physicians and patients from the main study. Results from the exploratory study will be analyzed separately from the main study results.

Procedures for the exploratory study will be similar to those in the main study (see [Section 3.1.1](#)), with the exception that there will be 1-month intervals of Abilify MyCite use (and 1-month intervals of prohibition of Abilify MyCite use), as diagrammed in the study schematic ([Figure 3.1-3](#)). During periods of nonuse of Abilify MyCite, the patient continues with oral aripiprazole, per routine clinical care.

In the exploratory study, each patient will receive Abilify MyCite per 1 one of 2 sequences over a 360-day period:

- Sequence 1: Only in Months 1, 2, 5, and 10.
- Sequence 2: Only in Months 1, 4, 7, and 10.

Sites will be randomized to 1 of the 2 sequences.

For this exploratory study, the site visits will be at screening, baseline (which may be the same day as the screening visit), Day 180, and Day 360; additional visits are to occur as clinically indicated. The exploratory arm will begin after the main study is enrolled at approximately 50% (ie, staggered start).

3.2 Study Population

Enrollment is described in [Section 3.2.1](#) (main study) and [Section 3.2.2](#) (exploratory study).

For information on the virtual matched control group, see [Section 3.5.4](#).

3.2.1 Main Study

The main study will enroll approximately 640 adult patients with SCH, BP1, or MDD who, within 60 days prior to study enrollment, had a hospitalization (all-cause or psychiatric, ie, for any reason) or at least 1 psychiatric partial hospital admission. To achieve balanced enrollment of the targeted diagnoses, a minimum enrollment of each diagnosis will be 25% or approximately 160 total patients.

3.2.2 Exploratory Study

The exploratory study will utilize different physicians and patients from the main study.

The exploratory study will enroll approximately 150 adult patients (75 per sequence) with SCH, BP1, or MDD who, within 60 days prior to study enrollment, had a hospitalization (all-cause or psychiatric) or at least 1 psychiatric partial hospital admission.

As with the main study, to achieve balanced enrollment of the targeted diagnoses, a minimum enrollment of each diagnosis will be 25%, or approximately 37 patients. The exploratory arm will begin after the main study is enrolled at approximately 50% (ie, staggered start).

3.3 Eligibility Criteria for Physicians and Patients (Main and Exploratory Studies)

All of Section 3.3 applies to both the main study and the exploratory study. The procedures refer to physicians and patients at the study sites; for information on the virtual matched control group, see [Section 3.5.4](#).

3.3.1 Informed Consent

An informed consent form (ICF) fully describing the purpose, procedures, and potential risks and benefits of the study will be developed and approved by the Institutional Review Board / Independent Ethics Committee (IRB/IEC) prior to study initiation. The study physician must ensure that each study patient is fully informed of the study and authorizes release of health information prior to study enrollment. Written informed consent will be obtained prior to initiation of any study-related procedures. The patient will receive a copy of the signed ICF. The study physician will retain the original signed ICF for each patient. The IRB/IEC must prospectively approve the ICF and any changes to the ICF during the course of the study before use.

3.3.2 Physician Practice Eligibility

Enrollment of approximately 100 physician sites overall (ie, main study plus exploratory study) from the Anthem Network of providers in the United States (US) is planned for this study. HealthCore will identify potential physicians for the study by analyzing  to  to identify physicians who provide care for a high volume of patients who potentially meet basic inclusion criteria sufficient to support study enrollment goals.

Physicians (and patients) in the main study will be distinct from those in the exploratory study.

3.3.3 Patient Recruitment and Eligibility

Patients will be recruited for enrollment when they interact with their physician as part of their standard of care. Eligible participants include adult patients with a current diagnosis of SCH, BP1, or MDD being treated with aripiprazole, or for whom aripiprazole treatment would be appropriate, as determined by the treating physician. Patients must also meet all of the inclusion criteria (Section 3.3.4) and none of the exclusion criteria (Section 3.3.5).

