3.5.1.2 Main Study: Enrollment Procedures

The study physician will make the decision regarding the patient's suitability for the study. The determination that a patient is appropriate for treatment with aripiprazole (regardless of whether or not they would switch from current treatment) and initiation of Abilify MyCite will be made prior to and independent of study initiation. Following the treating physician's determination of eligibility, patients will be approached for enrollment. As part of their routine office visits, patients will be approached for potential enrollment into the study by their treating physician.

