3.4 Virtual Matched Control Group

Enrolled patients will be matched to a virtual control group in a 1:3 ratio (enrolled patients on Abilify MyCite treatment : virtual matched controls). [REDACTED]

The matching process will be conducted after 6-month study data (or early termination data, if applicable) is collected for all Abilify MyCite patients. The virtual matched control group identified in this process will be used for all study analyses with a small amount of attrition expected for the 12-month analyses for controls who no longer have Anthem insurance coverage.

A pool of potential controls will first be identified using the following criteria:

- ≥ 1 day of enrollment in an Anthem-affiliated commercial, Medicaid, or Medicare health plan with medical and pharmacy benefits during the observation period (from date of First Patient In up until date of Last Patient In)¹³.
- ≥ 1 pharmacy claim for any atypical antipsychotic (excluding Abilify MyCite, clozapine, and long-acting injectable antipsychotics [LAIs]^{14,15}) during the observation period (Appendix F, Tables 2a and 2b).

¹³ Timeframe may be extended if additional samples are needed.

¹⁴ LAIs include: Aripiprazole monohydrate (Abilify Mantenna), Aripiprazole lauroxil (Aristada), Olanzapine pamoate (Zyprexa Relprevv), Paliperidone palmitate (Invega Sustenna), Paliperidone palmitate (Invega Tri state), Risperidone microspheres (Risperdal Consta)

¹⁵ Drugs include: Aripiprazole, Asenapine, Brexpiprazole, Cariprazine, Iloperidone, Paliperidone, Pimavanserin tartrate, Quetiapine fumarate, Risperidone, Ziprasidone, Ziprasidone Mesylate

- ≥ 1 all-cause hospitalization or partial psychiatric hospitalization¹⁶ that occurs at most 60 days prior to a pharmacy claim for any atypical antipsychotic (excluding Abilify MyCite, clozapine, and LAIs).
 - The earliest such pharmacy claim observed after the earliest observed hospitalization will be set as the initial (temporary) index date for each potential control.
 - For patients with ≥ 2 qualifying hospitalization/pharmacy claim episodes, an iterative process will be used to find the best match, and the final index date will be assigned accordingly.
- Age 18 to 63 on index date.
- ≥ 1 claim for SCH, BP1, or MDD on or before index date.
- No claims for pregnancy during the observation period.
- No claims for any LAI during the observation period.
- ≥ 180 days of medical and pharmacy enrollment prior to index date

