- ≥ 180 days of medical and pharmacy enrollment following index date

Prior to matching, the pool of potential controls and the Abilify MyCite cohort will be stratified by psychiatric diagnosis (SCH, BP1, MDD). The Abilify MyCite cohort psychiatric diagnosis will be based on the psychiatric diagnosis recorded in the eCRF. The potential controls psychiatric diagnosis will be based on the psychiatric diagnosis identified [REDACTED] CCI. In the event that more than one of the qualifying psychiatric diagnoses is identified [REDACTED] CCI, the following hierarchy will be applied to potential controls: SCH>BP1>MDD.

From this pool of patients, combined with the active arm, logistic regression will be used within each psychiatric diagnosis to estimate a propensity score for each patient, where propensity refers to a patient's pre-index likelihood to be in the active arm. The dependent variable equals 1 for patients in the active arm and 0 for the controls. The following variables may be considered for inclusion in the propensity score model; a final determination will be made using descriptive study results on patient baseline characteristics.

- Age
- Gender
- Month of index date
- Plan type (commercial, Medicaid, or Medicare health plan with medical and pharmacy benefits)
- Number of fills for any atypical antipsychotic over 6-12 months prior to index date
- [REDACTED] CCI
- Occurrence/number of visits with a psychiatrist over 6-12 months prior to index date
- Comorbidities over 6-12 months prior to index date

¹⁶ Defined as a medical claim with place of service code = 52 ("Psychiatric Hospitalization"), or with HCPCS codes H0035 or S0201.

- Region of patient residence (Northeast, South, Midwest, West)

The estimated propensity scores will be used to match active arm patients to the virtual controls in a 1:3 ratio. Prior to assessing outcomes, the validity of the propensity score adjustment will be assessed by (1) graphically examining the overlap in propensity scores across treatment and control groups¹⁷, and (2) comparing balance in all baseline characteristics across the cohorts via standardized mean differences. A standardized mean difference >10% in absolute value will be used to indicate potential imbalance that may warrant further investigation or adjustment (e.g. through regression analysis).¹⁸ Propensity score models will be finalized prior to the assessment of outcomes.

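### MyCite patients all enter through an office visit after a recent admission, while no visible control criterion requires outpatient contact after the admission; this probably favours MyCite

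*Protocol*

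**What the plan says.** **MyCite arm.** Protocol 3.3.3 places recruitment at a clinical contact: "Patients will be recruited for enrollment when they interact with their physician as part of their standard of care". Protocol 3.5.1.2 makes that contact an office visit: "As part of their routine office visits, patients will be approached for potential enrollment into the study by their treating physician". Protocol 3.1.1 starts the intervention at the baseline visit, where "Abilify MyCite onboarding will be provided in the office". Inclusion criterion 6 (Protocol 3.3.4) requires a hospitalization, or a psychiatric partial hospital admission, within 60 days before enrollment.

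**Control arm.** SAP 3.4 requires an all-cause or partial psychiatric hospitalization "that occurs at most 60 days prior to a pharmacy claim for any atypical antipsychotic". For the index date: "The earliest such pharmacy claim observed after the earliest observed hospitalization will be set as the initial (temporary) index date for each potential control". A patient with two or more qualifying episodes may later be moved to another one. The remaining criteria are plan enrollment, age 18 to 63, a claim for one of the three diagnoses, no pregnancy or long-acting injectable claims, and at least 180 days of enrollment on each side of index.

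**Matching.** The one visible visit covariate is "Occurrence/number of visits with a psychiatrist over 6-12 months prior to index date". It belongs to a list that opens with "The following variables may be considered for inclusion in the propensity score model", so its inclusion is not fixed.

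**The concern.** A patient who has reached a physician's office within 60 days of an admission has shown that he or she is back in outpatient care. Every MyCite patient meets that condition by the way patients are recruited. A control can qualify without it, since a prescription filled at discharge meets the fill requirement. If return to outpatient care predicts a lower chance of readmission, the MyCite arm starts with a lower expected hospitalization rate for a reason unrelated to the device. The primary endpoint is the proportion hospitalized by Day 180, so the entry difference feeds directly into it.

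Matching on days since admission would not remove this. On the same day after discharge, one patient is in a physician's office and the other may only have collected a prescription.

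**Working it through.** **1. Entry rules side by side**

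| | MyCite | Control |
|---|---|---|
| Recent admission | Yes, within 60 days of enrollment | Yes, within 60 days of the fill |
| Outpatient contact after admission | Yes, through recruitment | Not required by any visible criterion |
| Antipsychotic | Prescribed aripiprazole or appropriate for it | Must have filled an atypical antipsychotic |
| Start of follow-up | In-office baseline visit | Pharmacy claim |

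The psychiatrist-visit covariate closes the gap only in part. It is optional and covers one specialty. Read as a look-back of 6 to 12 months, it pools visits before the admission with visits after discharge. Read as months 6 to 12 before index, it misses the post-discharge period altogether. The 10% standardized-difference check can flag only what is measured.

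**2. The plan's own figure** (Protocol 7.1, SAP 4.2)

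Inputs: 29.04% versus 36.30% (difference 7.26 points), 1:3 matching, one-sided 0.025, 80% power.

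- Pooled-variance formula, p̄ = (0.2904 + 3 × 0.3630)/4 = 0.3449: n = [1.96·√(p̄(1−p̄)·4/3) + 0.8416·√(0.2904·0.7096 + 0.3630·0.6370/3)]² / 0.0726² = 441. The plan states 447, which is within 3%.
- Power at 447 versus 3 × 447 = 1341 is 80.6%.
- The unpooled formula that the text names, without continuity correction, gives 422. That difference does not affect this point.

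**3. Bias from the entry difference**

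Let u be the share of controls who did not return to outpatient care, and d the excess of their 180-day hospitalization rate over that of controls who did. If the device does nothing and matching removes none of the difference, the spurious benefit is u × d. Neither quantity is in the documents; both are assumed here.

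- u = 20%, d = 5 points: 1.0 point, or 1/7.26 = 14% of the planned effect.
- u = 50%, d = 10 points: 5.0 points, or 5/7.26 = 69% of it.

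**4. Effect on type I error**

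Using the independent two-proportion comparison of the sample-size section, SE = √[0.363 × 0.637 × (1/447 + 1/1341)] = 0.0263. One-sided error = P(Z > 1.96 − bias/0.0263):

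| Residual bias (points) | One-sided type I error |
|---|---|
| 0 | 2.5% |
| 1 | 5.7% |
| 2 | 11.5% |
| 3 | 20.7% |
| 5 | about 48% |

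**5. Cross-check with risk ratios**

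Let RR be the risk ratio of non-returners to returners, and hold the overall control rate at 36.3%. The rate among returners is then 0.363/(1 + u(RR − 1)).

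- u = 0.2, RR = 1.2: 34.9%, bias 1.4 points, error about 8%.
- u = 0.2, RR = 1.5: 33.0%, bias 3.3 points, error about 24%.
- u = 0.3, RR = 1.5: 31.6%, bias 4.7 points, error about 44%.
- u = 0.4, RR = 1.5: 30.3%, bias 6.1 points, error about 65%.
- RR = 1: no bias.
- u = 0.2, RR = 0.8: 37.8%, bias −1.5 points, against MyCite.

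The RR = 1.5 rows imply a larger d than step 3 assumes; at u = 0.2, d = 0.5 × 33.0 = 16.5 points.

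**6. Power if controls must also have returned to care**

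Keep the 20% relative reduction and 447 versus 1341. With control rates of 34.9%, 33.0%, 31.6% and 30.3%, pooled-formula power is 78.2%, 74.8%, 72.0% and 69.4%. Restoring 80% would take 467, 507, 540 or 573 completers.

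**The case against.** Several counter-arguments carry weight.

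- **Direction.** Every control must have filled an atypical antipsychotic, whereas a MyCite patient need only be prescribed aripiprazole or be suitable for it. Controls are thus selected on obtaining medication, which may offset part of the bias. This stands: the direction is a plausible inference. The protocol's own statement that engagement may benefit health outcomes (1.1) supports it, but no rate in the documents establishes it.
- **Who the non-returners are.** A reader might infer that controls without a visit before index never returned to care. The documents do not support that. The provisional index is the earliest qualifying claim, so a control indexed at a discharge fill may attend follow-up a week later. The share without a visit before index therefore mixes true non-returners with people indexed before they could attend, and the second group is partly an index-date problem.
- **Existing safeguards.** Prior fills, comorbidities, psychiatrist visits, balance checks and possible regression adjustment are all listed in SAP 3.4. They may remove some of the bias. None isolates contact after discharge.
- **Redaction.** One candidate covariate, other text in SAP 3.4 and the body of Protocol 3.5.4 are blacked out. The gap can be asserted only for the visible text.

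It would also be wrong to infer that a control needs nothing but a filled prescription; the other pool criteria apply. The accurate statement is that no visible criterion requires outpatient contact after the admission.

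**Conclusion.** The asymmetry is real on the visible text: the MyCite arm is selected on return to outpatient care after an admission and the control arm is not. The effect probably favours MyCite. Its size cannot be taken from the documents. The 1 to 5 points, and the 6% to 48% one-sided error that follows, illustrate assumed inputs with no correction by matching. A reader might take 48% as an estimate, but it is the far corner of two assumed ranges. The bias vanishes if non-returners have the same risk and reverses if theirs is lower.

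The gap is worth closing because a bias of even 1 point more than doubles the nominal 2.5% error, and the remedy uses claims of a kind the plan already draws on. SAP 5.0 records that the study stopped after two patients with no efficacy assessment, so no result is affected. The point concerns the design and any reuse of it.

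**What to change.** Change SAP 3.4 in three linked ways:

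1. Require each control to have at least one outpatient visit with a prescribing clinician after discharge from the qualifying admission and within 60 days of it.
2. Set the control index at the first qualifying antipsychotic claim on or after that visit, still within 60 days of the admission. Apply the same rule to every candidate episode in the iterative matching. Without this step, a control who filled at discharge and attended later would be dropped.
3. Make the number of post-discharge outpatient visits before index a required propensity covariate, with the entry visit left out in both arms. Leaving it out in the MyCite arm alone would build in a new imbalance: a MyCite patient screened at the first visit could count zero while every control counted at least one.

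**Cost.** SAP wording and additional claims queries. The control pool shrinks, which could trigger the fallback to 1:2 or 1:1 matching in SAP 4.2. At 1:1 the pooled formula needs 654 MyCite completers at the planned rates, against 441 at 1:3. The control event rate may also fall below 36.3%, with the loss of power shown in the working, so the sample size should be rechecked against the rate in the restricted pool.

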3.3.4 Patient Inclusion Criteria

For enrollment into the study, patients are required to meet the following inclusion criteria:

Table 3.3.4-1 Inclusion Criteria	
1.	Patients are actively enrolled in an Anthem-affiliated commercial, Medicaid, or Medicare health plan with medical and pharmacy benefits.
2.	Male and female patients between the ages of 18 and 63 years, inclusive at the time of consent.
3.	Patients must have a smartphone with data plan.
4.	Patients must have a current diagnosis of SCH, BP1, or MDD.
5.	Patients currently prescribed aripiprazole, or appropriate for aripiprazole treatment.
6.	Within 60 days prior to study enrollment, patients are required to have had a hospitalization (all cause or psychiatric) or at least 1 psychiatric partial hospital admission.
7.	Patients are deemed appropriate, per the study physician judgment, to use Abilify MyCite per the package insert and to enter this interventional study.
8.	Patients must be able to read and understand English.

3.3.5 Patient Exclusion Criteria

For enrollment into the study, patients will be excluded if they fall under any of the following exclusion criteria.

Table 3.3.5-1 Exclusion Criteria	
1.	Any patient who participated in another clinical trial within 30 days of enrollment into the current study.
2.	Females who are breast-feeding and/or who are pregnant at the time of study enrollment, or who plan to become pregnant during the study.
3.	Patients who are currently being treated with a long-acting injectable antipsychotic.

3.4 Outcome Variables

3.4.1 Primary Endpoint (Main Study)

The primary endpoint is the difference in the proportion of patients with all-cause hospitalizations for patients using Abilify MyCite versus virtual matched controls from baseline to Day 180.

3.4.2 Secondary Endpoints (Main Study)

The secondary endpoint is the difference between groups (Abilify MyCite versus virtual matched controls) in the proportion of patients with at least 80% proportion of days covered (PDC) (with antipsychotic medication) from baseline to Day 180.

